12.1 Prior Anti-Cancer Treatment and Procedures

The prior anti-cancer treatments and procedures are collected under the “PRIOR ANTI-CANCER SURGERIES”, “PRIOR ANTI-CANCER DRUG THERAPIES”, “PRIOR ANTI-CANCER RADIOTHERAPY”, eCRF pages.

The overall summary of presence of prior anti-cancer treatments/procedures tables will include:

- Number of subjects with at least one prior anti-cancer drug therapy
 - Type of therapies: Cytotoxic therapy / Endocrine therapy / Monoclonal antibodies therapy / Molecular Target Therapy / Immunotherapy / Other
 - Intent of therapy: Neoadjuvant / Adjuvant / Metastatic or Locally advanced
 - Best response: Complete Response (CR) / Partial Response (PR) / Stable Disease (SD) / Progressive Disease (PD) / Non-Complete Response/Non-Progressive Disease (Non CR/ Non PD) / Not Evaluable / Unknown
 - Time since documented progression disease (months)
- Number of subjects with at least one prior radiotherapy
 - Total dose (Gy), (mCi)
 - Number of fractions
 - Best response: Complete Response (CR) / Partial Response (PR) / Stable Disease (SD) / Progressive Disease (PD) / Non-Complete Response/Non-Progressive Disease (Non CR/Non PD) / Not Evaluable / Unknown
- Number of subjects with at least one prior anti-cancer surgery
 - Curative intent for surgery: yes/no
 - Outcome of surgery: No residual tumor after resection (R0) / Tumor/metastases not resected completely with microscopic residual lesions (R1) / Tumor/metastases not resected completely with macroscopic residual lesions (R2) / Metastases not resected (NR) / Other

The following listings of prior anti-cancer treatments and procedures will also be provided:

- Listing of prior anti-cancer drug therapies
- Listing of prior surgeries
- Listing of prior radiotherapy

12.2 Prior or Concomitant Medication and Procedures

Medications

Concomitant medications are medications, other than trial medications, which are taken by subjects any time on-trial (on or after day 1 of treatment); Or any medication which are taken within 30 days after last dose of trial drug. Prior medications are medications, other than trial medications and premedications, which started and stopped before administration of trial drug.

Prior and Concomitant medications will be summarized from the “CONCOMITANT MEDICATIONS DETAILS” eCRF page. ATC-2nd level and PT will be tabulated as given from the WHO-DD dictionary current version. In case multiple ATC’s are assigned to a drug, all ATC-2nd level will be used for reporting. Prior and Concomitant medications will be listed. The listing will include: subject identification number, dose level/cohort and all corresponding collected data-field on the corresponding eCRF pages, as well as a flag to identify each medication as Prior or Concomitant.

Incomplete prior/concomitant medication dates will be imputed as follows:

- If the medication date is missing completely, then the medication date will be replaced by the start of study treatment.
- If the day of medication date is missing, but the month and year are equal to the start of study treatment, then the medication date will be replaced by the start of study treatment. For example, if the medication start date is --/JAN/2015, and study treatment start date is 15/JAN/2015, then the imputed medication start date will be 15/JAN/2015.
- If both the day and month of medication start date are missing but the start year is equal to the start of study treatment, then the medication date will be replaced by the start of study treatment. For example, if the medication start date is --/---/2014, and study treatment start date is 19/NOV/2014, then the imputed medication start date will be 19/NOV/2014.
- In all other cases the missing medication day or missing medication month will be replaced by 1.
- Incomplete stop date will be replaced by the last day of the month (if day is missing only), if not resulting in a date later than the date of patient's death. In the latter case the date of death will be used to impute the incomplete stop date.
- In all other cases the incomplete medication stop date will not be imputed.

Procedures

Prior and concomitant status for Procedures is defined using the same rule as for medications.

Prior and Concomitant procedures will also be listed including: subject identification number, cohort and all corresponding collected data-field on the corresponding eCRF page. A flag will be added to identify each procedure as Prior or Concomitant.

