11.3 Other Baseline Characteristics

Information of other baseline characteristics collected at the baseline evaluation visit will be summarized in total and by dose level/cohort. Summary statistics will be presented for:

- Serology: Hepatitis B, hepatitis C, and HIV tests
- Nicotine use status: Never, Regular, Occasional, Former
- Nicotine Consumption: summary statistics
- Alcohol use status: Never, Regular, Occasional, Former
- ECOG performance status
 - 0: Fully active, able to carry on all pre-disease performance without restriction.
 - 1: Restricted in physically strenuous activity but ambulatory and able to carry out work of a light or sedentary nature, e.g., light house work, office work.
 - 2: Ambulatory and capable of all self-care but unable to carry out any work activities. Up and about more than 50% of waking hours.
 - 3: Capable of only limited self-care, confined to bed or chair more than 50% of waking hours.
 - 4: Completely disabled. Cannot carry on any self-care. Totally confined to bed or chair.
 - 5: Dead.

Baseline characteristics with respect to vital signs, physical examinations, and hematology/biochemistry will be part of Section 15.

Disease history

Disease history is collected in “DISEASE HISTORY” pages.

Summary statistics for the following parameters will be presented by treatment dose

- Site of primary tumor

- Metastatic sites
- Time since initial diagnosis (months)
- Time since documented, locally advanced, inoperable or metastatic disease (months)
- TNM classification at initial diagnosis: each T, N, M category will be described (TX, T0, N1, etc.)
- TNM classification at study entry

Specifications for computation:

- Time since initial cancer diagnosis (months) = (date of first avelumab administration – date of initial cancer diagnosis)/30.4375
- Time since documented, locally advanced, inoperable or metastatic disease (months) = (date of first avelumab administration – date of documented, locally advanced, inoperable or metastatic disease)/30.4375
- Time since progression disease (months) = (date of first administration – date of progression disease) / 30.4375

Incomplete dates for disease history (initial diagnosis date, date of documented, locally advanced, inoperable or metastatic disease diagnosis, date of response or progression in prior treatment) will be imputed as follows:

- If the day is missing, it will be imputed to the 15th day of the month.

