- **Adverse Events Leading to Death:** adverse event leading to death (as recorded on the AE eCRF page, Outcome = Fatal, as well as AEs of Grade 5).
- **Related AE Leading to Death**
- **Immune Related Adverse Events (irAE):** immune related adverse events are identified via customized MedDRA PT queries and additionally classified by investigator according to case definition (two level approach). Details are included in Appendix 18.2.
- **Infusion Related Reactions (IRR):** IRRs are identified based on a list of MedDRA PTs. The detailed criteria of the timing relationship to infusion are specified in Appendix 18.2.

Incomplete AE-related dates will be handled as follows:

- Incomplete or missing start date:
 - In case the onset date is completely missing or the onset is in the same year (if the onset year is available only) or the onset is in the same month and year (if the day is missing) as start of study treatment, then the onset date will be replaced by the minimum of start of study treatment date and AE resolution date (imputed, if incomplete).
 - In all other cases the missing onset day or onset month will be replaced by 01.
- Incomplete or missing stop date:

- Incomplete stop dates will be replaced by the last day of the month (if day is missing only), if not resulting in a date later than the date of subject's death. In the latter case the date of death will be used to impute the incomplete stop date.
- In all other cases, the incomplete stop date will not be imputed.

AEs will be coded using the latest version of Medical Dictionary for Regulatory Activities (MedDRA). The severity of AEs will be graded by the investigator using the NCI-CTCAE version 4.03.

The AE reporting period for safety surveillance begins when the subject is included in the study (date of first signature of informed consent) and continues for all SAEs and treatment-related non-serious AEs through to the study's Safety Follow-up Phone Call, defined as 90 days (\pm 7 days) after the last administration of avelumab. Any SAE suspected to be related to avelumab must be reported whenever it occurs, irrespective of the time elapsed since the last administration of avelumab.

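### SAP 12.2 sets an unknown medication start to first dose even when the drug had already stopped, so the start falls after the stop and the record is no longer prior

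*SAP*

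**What the plan says.** SAP 12.2 sets a medication start to the first-dose date in three situations:

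- nothing is known: "If the medication date is missing completely, then the medication date will be replaced by the start of study treatment";
- only the day is unknown: "If the day of medication date is missing, but the month and year are equal to the start of study treatment";
- day and month are unknown: "If both the day and month of medication start date are missing but the start year is equal to the start of study treatment".

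Any other missing day or month becomes 1. A stop date lacking only its day becomes the last day of the month, limited by the date of death; other incomplete stops are left alone. None of the start rules mentions the stop date.

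The same section defines prior medications as those "which started and stopped before administration of trial drug", and concomitant medications as those "taken by subjects any time on-trial (on or after day 1 of treatment") or within 30 days after the last dose. Procedures are tied to this: "Prior and concomitant status for Procedures is defined using the same rule as for medications".

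The adverse event rule in SAP 15.2 has the same three triggers but a different result: "then the onset date will be replaced by the minimum of start of study treatment date and AE resolution date", with the resolution date itself imputed if incomplete.

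For disease-history dates, including response or progression on earlier treatment, SAP 11.3 says: "If the day is missing, it will be imputed to the 15th day of the month". No upper limit at first dose is given.

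**The concern.** Setting an unknown start to first dose is a reasonable cautious convention when nothing shows that the drug ended earlier. When the stop is known, or can be imputed, and lies before first dose, the same rule contradicts collected data. The SAP applies a safeguard for adverse events and leaves it out for medications, which reads as an oversight. According to its modification history, the medication-date rule was added in Final 2.0.

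Such records are foreseeable. Protocol 7.2.3 collects medications taken within 30 days before screening, and exclusion criterion 11 requires most subjects on immunosuppressive agents to be tapered off before avelumab. Drugs with a clear stop shortly before Day 1 and an uncertain start can be expected.

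What is at stake is the prior/concomitant flag in the tables and listings and, possibly, a false hit in the programmatic part of PDEV10 (SAP Appendix 18.1), the important deviation for prohibited medication. With about 21 to 24 subjects and Q2W dose levels of 3 or 6, one misclassified subject is 1/3 = 33% or 1/6 = 17% of a cohort column.

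**Working it through.** **Reproducing the SAP's figures.** Section 12.2 gives two worked examples. A start of --/JAN/2015 with first dose 15/JAN/2015 becomes 15/JAN/2015. A start of --/---/2014 with first dose 19/NOV/2014 becomes 19/NOV/2014. Both follow from the rules as written.

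**Adding a stop date.** The stop dates below are assumptions, since the SAP examples give none. The gap is imputed start minus stop; the capped start is min(first dose, stop).

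| Recorded start | First dose | Assumed stop | Start under 12.2 | Gap | Capped start |
|---|---|---|---|---|---|
| --/JAN/2015 | 15 Jan 2015 | 10 Jan 2015 | 15 Jan 2015 | 5 days | 10 Jan 2015 |
| missing | 15 Jan 2015 | 10 Jan 2015 | 15 Jan 2015 | 5 days | 10 Jan 2015 |
| missing | 15 Jan 2015 | 20 Dec 2014 | 15 Jan 2015 | 26 days | 20 Dec 2014 |
| --/---/2014 | 19 Nov 2014 | 30 Jun 2014 | 19 Nov 2014 | 142 days | 30 Jun 2014 |

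A partial stop behaves the same way. With start missing, first dose 15 January 2015 and stop --/DEC/2014, the stop is imputed to 31 December 2014 and the start to 15 January 2015, 15 days later.

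**Classification.** Prior needs start < first dose and stop < first dose. In every row the imputed start equals first dose, so the first condition fails although the stop is earlier. The record is not clearly concomitant either, because the retained stop date says that the drug was not taken on or after Day 1. The SAP has no rule for a record that meets neither definition. With the capped start, all four rows satisfy both conditions and are prior.

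**Disease history (secondary).** SAP 11.3 computes time since event as (first dose − event date)/30.4375. With the day missing and the event in the month of first dose, the event date becomes the 15th:

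- first dose on the 1st: (1 − 15)/30.4375 = -0.46 months;
- first dose on the 5th: (5 − 15)/30.4375 = -0.33 months;
- first dose on the 14th: (14 − 15)/30.4375 = -0.03 months;
- first dose on the 15th or later: zero or positive.

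The rules for a missing month (July 1st for an earlier year, January 1st for the year of first dose) cannot pass first dose. The fault lies in the 15th-of-month rule alone. SAP 12.1 plans a summary of time since documented progression, so a negative value would enter a table.

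**The case against.** The best reply is that little follows in practice, and several stronger readings that a reader might infer do fail.

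- *A prior anticancer drug would appear as concomitant.* Not supported. SAP 12.1 takes prior anticancer drugs, radiotherapy and surgery from their own eCRF pages, whereas the 12.2 summary uses the concomitant-medication page. Steroids and other general medications are the relevant case.
- *Prior drugs necessarily become concomitant.* Not stated. The inverted record meets neither definition, and becomes concomitant only if the flag is set from the start date.
- *False important deviations would be reported.* PDEV10 allows medical review as well as a programmed check, SAP 8.1 has important deviations confirmed by the Data Review Meeting, and SAP 9.3.5 flags imputed values in listings. Nothing says that PDEV10 uses imputed starts.
- *Negative medication durations would be tabulated.* SAP 12.2 plans no medication duration.

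The disease-history case is also narrow. The event must fall in the month of a first dose given on days 1 to 14, so at most 14 − 1 = 13 days earlier, with the day unknown. That lies inside the 14-day screening window of Protocol 7.1.1, when tumor history is being documented. The general 28-day washout makes progression during the previous therapy in that month rarer still. Days 1 to 14 make up 14 × 12 / 365 = 46% of the calendar, but that share is conditional on such an event and is not a frequency.

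All of this limits the consequences. It does not remove the inverted dates or the failed prior definition, which come from applying 12.2 exactly as written.

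**Conclusion.** The point holds as a minor correction. When a known or imputable stop precedes first dose, SAP 12.2 produces a start later than the stop, and the drug fails the SAP's own test for prior. In the examples the gap is 5 to 142 days, depending entirely on the assumed stop. Tabulation as concomitant, or a temporary PDEV10 hit, is possible but depends on programming that the SAP does not specify.

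The negative time since event, from -0.03 to -0.46 months, is real but rare and secondary.

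The documents give no frequency of incomplete dates, so the number of affected records cannot be estimated. The effect is confined to descriptive tables and listings; the DLT and PK analyses do not use these dates.

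**What to change.** In SAP 12.2, wherever the start is now set to first dose, set it to the minimum of the first-dose date and the stop date (imputed if incomplete), as SAP 15.2 does for adverse events. Add one sentence: a stop before first dose means prior, whatever is known about the start. Procedures follow, since they share the prior/concomitant rule.

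In SAP 11.3, add that an imputed disease-history date may not be later than first dose. Time since event is then never below zero.

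The cost is a few lines of SAP text and the matching derivation code. No new data, protocol change or change to the primary analyses is needed.

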12.3 Anti-cancer Post-treatment

The data collected from the “ANTI-CANCER TREATMENT AFTER DISCONTINUATION, RADIOTHERAPY AFTER DISCONTINUATION DETAILS and SURGERY AFTER DISCONTINUATION DETAILS” eCRF page will be listed.

The anti-cancer treatments after discontinuation will also be summarized in terms of:

Number of subjects with at least one anti-cancer drug therapy after discontinuation

- Type of therapies: Cytotoxic therapy / Endocrine therapy / Monoclonal antibodies therapy / Small molecules / Immunotherapy / Other
- Intent of therapy: Neoadjuvant / Adjuvant / Metastatic or Locally advanced
- Best response: Complete Response (CR) / Partial Response (PR) / Stable Disease (SD) / Progressive Disease (PD) / Non-Complete Response/Non-Progressive Disease (Non CR / Non PD) / Not Evaluable/ Unknown

13 Treatment Compliance and Exposure

Analysis Sets: Safety analysis set

13.1 Pre-medication

The number of subjects receiving pre-medication will be summarized for each treatment visit based on “PREMEDICATION DETAILS” eCRF page (subjects for whom the question “Has the subject received premedication before avelumab infusion?” (eCRF PREMEDIATION) is answered “Yes” at the corresponding visit). Percentages will be calculated on the number of subjects who actually received an infusion at the associated visit. In addition, a listing of premedication displaying dose cohort, subject identifier, date and time of administration, name of treatment, dose, unit and route of administration will be provided.

13.2 Exposure to Study Drug

The extent of exposure for avelumab will be characterized by duration (weeks), number of administrations, cumulative dose (mg/kg), dose intensity (mg/kg/cycle), relative dose intensity, number of dose delays.

Descriptive statistics will be used to summarize treatment exposure, based on the data being collected in “AVELUMAB ADMINISTRATION DETAILS” page of eCRF. Summaries will be performed on the safety analysis set. Subjects will receive an IV infusion of avelumab (over 1 hour

[- 10 minutes/+ 20 minutes, i.e., 50 to 80 minutes]) once every 2 weeks or, if 20 mg/kg once every 2 weeks have been established, 10 mg/kg every week for the first 12 weeks and once every 2 weeks thereafter starting at Week 13.

Safety analyses will be performed on the Safety Analysis Set. The safety endpoints will be tabulated by dose level and cohort, using descriptive statistics.

(1) Avelumab (3, 10, 20 mg/kg) once every 2 weeks (Q2W):

- **The duration of avelumab (weeks)** during the study is defined as:

$$\left(\frac{\text{date of last dose of avelumab} - \text{date of first dose of avelumab} + 14}{7} \right)$$

- **The cumulative actual treatment dose (mg/kg)** of avelumab per subject is the sum of the calculated actual dose levels of avelumab that the subject received (i.e. total dose administered (mg/kg)).
- **The dose intensity of avelumab (mg/kg/cycle)** per subject is defined as:

$$\left(\frac{\text{Cumulative dose of avelumab}}{0.5 * [(\text{date of last dose of avelumab} - \text{date of first dose of avelumab} + 14) / 7]} \right)$$

- **Total number of infusions received (n)**
- **Relative dose intensity of therapy (%):** The relative dose intensity per cycle is defined as $100 \times \text{actual dose intensity per cycle (mg/kg/cycle)} / (\text{planned dose level per cycle (mg/kg/cycle)})$

(2) Avelumab (10 mg/kg) once weekly (Q1W) for 12 consecutive weeks and then starting at Week 13, once every 2 weeks (Q2W):

- **The duration of avelumab (weeks) for first 12 weeks receiving Q1W dose per subject** is defined as:

$$\left(\frac{\text{Date of last dose of avelumab(Q1W)} - \text{date of first dose of avelumab(Q1W)} + 7}{7} \right)$$

- **The duration of avelumab (weeks) for subsequent weeks receiving Q2W dose per subject** is defined as:

$$\left(\frac{\text{Date of last dose of avelumab(Q2W)} - \text{date of first dose of avelumab(Q2W)} + 14}{7} \right)$$

- **The cumulative actual treatment dose (mg/kg) of avelumab receiving Q1W dose** per subject is the sum of the calculated actual dose levels of avelumab that the subject received of Q1W dose (i.e. total Q1W dose administered (mg/kg)).
- **The cumulative actual treatment dose (mg/kg) of avelumab receiving Q2W dose** per subject is the sum of the calculated actual dose levels of avelumab that the subject received of Q2W dose (i.e. total Q2W dose administered (mg/kg)).
- **The dose intensity of avelumab (mg/kg/cycle) for first 12 weeks receiving Q1W dose per subject** is defined as:

$$\left(\frac{\text{Cumulative dose of avelumab (Q1W)}}{(\text{date of last dose of avelumab(Q1W)} - \text{date of first dose of avelumab(Q1W)} + 7) / 7} \right)$$

- **The dose intensity of avelumab (mg/kg/cycle) for subsequent weeks receiving Q2W dose per subject** is defined as:

$$\left(\frac{\text{Cumulative dose of avelumab (Q2W)}}{0.5 * [(\text{date of last dose of avelumab(Q2W)} - \text{date of first dose of avelumab(Q2W)} + 14) / 7]} \right)$$

- **Total number of infusions received (n) for Q1W dose and Q2W dose, respectively**
- **Relative dose intensity of therapy (%) for Q1W dose:** The relative dose intensity per cycle is defined as $100 \times \text{actual dose intensity per cycle (mg/kg/cycle) for Q1W dose} / (\text{planned dose level per cycle (mg/kg/cycle) for Q1W dose}$
- **Relative dose intensity of therapy (%) for Q2W dose:** The relative dose intensity per cycle is defined as $100 \times \text{actual dose intensity per cycle (mg/kg/cycle) for Q2W} / (\text{planned dose level per cycle (mg/kg/cycle) for Q2W dose}$.

Dose reduction is not allowed per protocol and will not be summarized.

Per protocol, Avelumab will be administered as 1-hour intravenous infusion. Subjects will receive the trial treatment once every 2 weeks (excluding 10 mg/kg once weekly cohort). Dose delays will be grouped into the following categories based on the deviation of the actual to the planned treatment administration day (relative to the previous non-zero dose date): no delay (including 1-2 days delays), 3-6 days delay, 7 or more days delay. For example, if one subject receives the study drug on day 1, then the next study drug administration date will be on day 15; however, if the

subject receives the study drug at day 16 or 17, this is considered as ‘no delay’. Any zero dose prior to the last treatment administration is considered as a dose interruption.

The summary of dose delays will be based on the safety analysis set and include the following categories:

- No delay
- 3-6 days delay
- 7 or more days delay

The categorization is based on the maximum length of delay, i.e. the worst case of delay if subjects have multiple dose delays.

[figure not shown]
A listing of study drug administration will include subject identifier, assigned dose level/cohort, number of days relative to previous administration date, dose delay (yes/no), duration of administration and other relevant information collected on the Avelumab Administration Details eCRF page.

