ADA: antidrug antibody; AE: adverse event; CR: complete response; CT: computed tomography; D: Day; DLT: dose-limiting toxicity; ECG: electrocardiogram; ECOG PS: Eastern Cooperative Oncology Group performance status; EOT: End-of-Treatment; hCG: human chorionic gonadotropin; HIV: Human immunodeficiency virus; ICF: Informed consent form; IMP: investigational medicinal product; MRI: magnetic resonance imaging; PD: progressive disease; CCI: [redacted] PK: pharmacokinetics; PR: partial response; RECIST: response evaluation criteria in solid tumors; SAE: serious adverse event; T4: thyroxine; TSH: thyroid-stimulating hormone; V: Visit; W: Week.

1. A time window of up to 3 days before or 1 day after the scheduled visit day (- 3/+ 1 days) is permitted for all study procedures (except for PK sampling visits on Day 2 and 3, see [Table 1-3](#)). The calculation of the dose of avelumab will be based on the weight of the subject determined within 72 hours prior to the day of drug administration.
2. All subjects will have an EOT Visit within 7 days after the decision to discontinue avelumab. In addition, subjects will be followed every 12 weeks ( $\pm 7$  days) for survival (including assessment of any further anticancer therapy).

CCI

[figure not shown]
4. If another anticancer therapy is administered before the end of this 7-day period, the EOT Visit should be conducted prior to the start of this new therapy, if possible. The EOT Visit may be performed on the day of the decision to discontinue avelumab.

CCI

7. Medical history should include history of cancer, previous and ongoing medications, previous surgeries, radiotherapies, baseline medical conditions, smoking and alcohol history, and family cancer history.
8. A full physical examination will be conducted at Clinical Screening, at the EOT Visit and at the 30-day Safety Follow-up Visit. During the Treatment Phase, the physical examination will be symptom-directed.
9. If the Clinical Screening ECOG PS was performed within 3 days prior to Day 1, it does not have to be repeated at Visit 1/Cycle 1 Day 1.
10. Enrolment will be done after confirmation that the subject meets all screening inclusion criteria ([Section 5.3.1](#)) without matching any exclusion criterion ([Section 5.3.2](#)).

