### 5.1.3.1 Adverse Drug Reactions Requiring Treatment Discontinuation or Modifications

The following adverse drug reactions (ADRs) require permanent discontinuation or treatment modification of avelumab treatment:

- Any Grade 4 ADRs: permanently discontinue avelumab except for laboratory values out of normal range that do not have any clinical correlation.
- Any Grade 3 ADRs:
  - Withhold avelumab except for laboratory values out of normal range that do not have any clinical correlate.
  - Permanently discontinue avelumab if toxicity does not resolve to Grade  $\leq 1$  or baseline within 12 weeks of last administration or if the same Grade 3 toxicity recurs (consider consult with the medical monitor before permanently discontinuing the treatment).
- Infusion should not be given if ECOG performance status is  $\geq 3$  on the day of study treatment administration. Treatment should be discontinued if ECOG performance status has not improved to  $\leq 2$  by the next scheduled treatment administration.
- Any Grade 2 ADRs should be managed as follows:
  - Infusion should not be given in case of ongoing Grade 2 ADR on the day of study treatment administration.
  - Treatment can be resumed according to original schedule\* once ADR resolved to Grade  $\leq 1$ . Up to 2 subsequent study drug doses may be omitted. If more than 2 doses are skipped, treatment may be resumed after consultation with the Medical Monitor.

\*Original schedule is defined as “the dosing schedule calculated according to first dose”.

If dosing is delayed more than 4 weeks, treatment may be resumed after consultation with the study Medical Monitor. Any delay in dosing in excess of 12 weeks is not permitted.

Infusion-related reactions and irAEs should be handled according to the guidelines provided in Sections 6.5.5.1 and 6.5.5.2, respectively.

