### 8.5.3 Analysis of Secondary and Safety Endpoints

#### 8.5.3.1 Analysis of Safety Endpoints

The extent of exposure to avelumab will be characterized by duration (weeks), number of administrations, cumulative dose (mg/kg), dose intensity (mg/kg/week), relative dose intensity (actual dose given/planned dose), number of dose reductions, and number of dose delays.

Safety analyses will be performed on the Safety Analysis Set. The safety endpoints will be tabulated by dose level and cohort, using descriptive statistics.

Safety assessments will be based on review of the incidence of AEs, ADRs, and changes in vital signs, ECGs, body weight, and laboratory values (hematology and serum chemistry).

The on treatment period is defined as the time from the first administration of avelumab to the last administration of avelumab date plus 30 days or the earliest date of subsequent anticancer drug therapy minus 1 day, whichever occurs first.

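### Two exposure derivations in SAP 13.2 can misreport delivered dosing: weekly-phase relative dose intensity ignores missed final weekly doses, and delays are measured from the previous dose instead of the visit schedule

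*SAP*

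**What the plan says.** **Dose intensity.** Protocol 8.5.3.1 lists "relative dose intensity (actual dose given/planned dose") among the exposure measures. For the weekly cohort, SAP 13.2 splits exposure into a weekly and a 2-weekly phase. "The dose intensity of avelumab (mg/kg/cycle) for first 12 weeks receiving Q1W dose per subject" is the cumulative weekly dose divided by (last weekly dose date − first weekly dose date + 7)/7. Relative dose intensity is 100 times that figure over the planned dose level per cycle. The 2-weekly phase has its own clock, which starts at its first dose.

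**Delays.** SAP 13.2 classes delays "based on the deviation of the actual to the planned treatment administration day (relative to the previous non-zero dose date"). The categories are "no delay (including 1-2 days delays), 3-6 days delay, 7 or more days delay". Its example: "if one subject receives the study drug on day 1, then the next study drug administration date will be on day 15". For each subject, "The categorization is based on the maximum length of delay". A zero dose before the last administration counts as an interruption.

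**Schedule.** Protocol Table 1-1 fixes visits at Days 1, 15, 29, 43 and so on. Its footnote 1 allows "A time window of up to 3 days before or 1 day after the scheduled visit day". Table 1-2 footnote 1 gives the weekly cohort a window of 1 day either side during weekly dosing and the same −3/+1 window from Week 13. Protocol 5.1.3.1, on resuming after a Grade 2 reaction, defines the original schedule as "the dosing schedule calculated according to first dose".

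**The concern.** The weekly cohort is there to assess the safety of more frequent dosing and has no DLT assessment, so how much of the weekly phase was delivered is part of its tolerability description. A relative dose intensity that drops when doses are missed in the middle of the phase, but not when the same number are missed at the end, does not measure delivery.

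The delay rule uses a rolling reference, while visits are fixed to Day 1. The two disagree whenever a dose is given early within its window. Because the worst delay sets the subject's category, one such pair of visits is enough to label a fully compliant subject as delayed. In a six-subject cohort that moves the table by 1/6, or 16.7 percentage points.

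**Working it through.** **Plan's own figures first.** With the previous dose on Day 1 and a 14-day interval, doses on Days 15, 16 and 17 deviate by 0, 1 and 2 days (no delay), as in the SAP example. Day 18 deviates by 3 days and enters the 3-6 day category. Full weekly dosing on Days 1 to 78 gives 120 mg/kg over (78 − 1 + 7)/7 = 12 weeks = 10 mg/kg/week, so relative dose intensity is 100%. Both rules work for a fully dosed subject.

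**Weekly relative dose intensity, subject rolls over on Day 85.** Inputs: 12 planned weekly doses of 10 mg/kg (Protocol 5.1.1.1) and the SAP 13.2 formula.

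| Weekly doses missed | Last weekly dose | Dose given (mg/kg) | SAP denominator (weeks) | SAP result | Given/planned |
|---|---|---|---|---|---|
| last 1 | Day 71 | 110 | (71−1+7)/7 = 11 | 100% | 110/120 = 91.7% |
| last 3 | Day 57 | 90 | (57−1+7)/7 = 9 | 100% | 90/120 = 75% |
| last 6 | Day 36 | 60 | (36−1+7)/7 = 6 | 100% | 60/120 = 50% |
| 3 in mid-phase | Day 78 | 90 | (78−1+7)/7 = 12 | 75% | 90/120 = 75% |

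With the last 3 missed, the weekly clock covers Days 1 to 63 and the 2-weekly clock starts on Day 85. The 21 days from Day 64 to Day 84 enter neither phase. Four 2-weekly doses from Day 85 then give 40/(0.5 × 8) = 10 mg/kg/cycle, again 100%.

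If one of six subjects misses the last three weekly doses and the others miss none, the mean by given/planned dose is (5 × 100 + 75)/6 = 95.8%. The SAP reports 100%.

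**Delay rule.** Deviation = actual day − (previous non-zero dose day + 14).
- Days 1, 12, 29: 29 − 12 − 14 = 3, a 3-6 day delay, although Day 12 is in window and Day 29 is exactly on schedule.
- The −3/+1 window has five days, so 5 × 5 = 25 consecutive pairs. Three reach 3 days or more: (−3, 0) = 3, (−3, +1) = 4 and (−2, +1) = 3.
- Weekly cohort from Week 13: Day 82 then Day 99 gives 99 − 82 − 14 = 3, the same result.
- Drift: Days 1, 17, 33, 49 each deviate by 2 and count as no delay, yet fall 2, 4 and 6 days after Days 15, 29 and 43.
- One omitted dose (Days 1, 29): 29 − 1 − 14 = 14, so the resumed dose falls in the category of 7 or more days although it is on schedule. If the omission is recorded as a zero dose, it also counts as an interruption.

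**How often compliant subjects would be flagged.** The documents give no visit-timing data, so this is an assumption shown as a range. First dose on Day 1, six later doses (Days 15 to 85), independent visit offsets; the result is the probability that at least one pair differs by 3 days or more.

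| Off-day visits fall | 85% on day | 70% on day | 50% on day |
|---|---|---|---|
| all within 1 day | 0% | 0% | 0% |
| +1: 40%, −1: 40%, −2: 15%, −3: 5% | 4% | 9% | 16% |
| evenly over −3, −2, −1, +1 | 17% | 29% | 42% |

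With all five window days equally likely the share is 51.5%. As a check, only the five pairs after the first can be flagged, each with probability 3/25 = 12%, so the share cannot exceed 60%.

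**The case against.** **The shortfall is not hidden.** SAP 13.2 also reports weekly-phase duration, cumulative weekly dose and number of weekly infusions. Nine infusions and 90 mg/kg against 12 and 120 can be seen. Protocol 8.5.3.1 does not state the period for planned dose, and 8.5.1 leaves details to the SAP. For a subject who stops for good, ending at the last dose plus one interval is a usual convention. All of this stands. It limits the error to subjects who roll over, and those subjects still get a wrong relative dose intensity.

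**The previous dose is a legitimate reference.** Protocol 5.1.3 counts its 4-week limit from the previous dose, and the first-dose definition in 5.1.3.1 concerns resumption after a Grade 2 reaction only. An interval does describe a treatment gap, and after an omitted dose that gap is real. So the choice of anchor is partly a matter of preference. What remains is that a table of delays flags doses the visit schedule permits.

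**Stronger readings that the documents do not support.** A reader might infer that on-schedule doses are generally coded as delays. Between in-window visits, it takes a preceding dose 2 or 3 days early. A reader might also infer that false delays arise only in the 2-weekly cohorts and so distort a comparison of regimens. During weekly dosing the ±1 day window indeed produces no such pair, but from Week 13 the weekly cohort has the −3/+1 window too. SAP 13.2 introduces delays with 2-weekly dosing, sets the weekly cohort aside and states no weekly-phase rule. No formal comparison of regimens on delays is planned; Protocol 8.5.1 makes the presentation descriptive.

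**Conclusion.** The point holds as two derivation errors in descriptive exposure tables. The DLT, PK and TEAE endpoints are unaffected.

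The dose-intensity error is the main one. It is exact and needs no assumption beyond a subject missing terminal weekly doses and then starting 2-weekly dosing: 100% reported against 91.7%, 75% or 50% for 1, 3 or 6 missed doses. How many of the six subjects would do this cannot be known from the documents.

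The delay error is secondary. The misclassified pairs are certain (3 of 25), but their frequency is not: 0% of compliant subjects if off-day visits stay within 1 day, about 4% to 16% if early visits are mostly 1 day early, and about 17% to 51.5% if they are spread evenly over the window. These figures also assume independent visits. The rule errs in the other direction too, because it misses cumulative drift.

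**What to change.** **Weekly relative dose intensity.** For subjects who receive any 2-weekly dose: 100 × cumulative weekly dose / 120 mg/kg (12 planned doses of 10 mg/kg). For subjects who stop for good in the weekly phase, keep the last dose + 7 days convention.

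**Delays.** Measure each delay against the scheduled day of the visit at which the dose is given, indexed by scheduled visit v and not by the number of doses administered, so that one omission does not shift every later dose:
- 2-weekly cohorts: Day 1 + 14(v − 1).
- Weekly cohort: Day 1 + 7(v − 1) up to visit 13 (Day 85), then Day 85 + 14(v − 13). This gives Days 99, 127 and 169 for visits 14, 16 and 19, matching Weeks 15, 19 and 25.

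Keep the existing categories, state that they apply to the weekly phase as well, count omitted doses separately as interruptions, and keep the interval since the previous dose in the listing. Days 1, 12, 29 then show no delay, and Days 1, 17, 33, 49 show delays of 2, 4 and 6 days.

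**Cost.** SAP wording and programming on dates already collected. No dosing rule or visit changes. Relative dose intensity will be lower for rollover subjects who missed final weekly doses.
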